14.0 STOPPING RULES

A dose-limiting toxicity will be defined as any grade 3 or 4 events which are at least possibly related to study product or administration procedure. If the first patient in a cohort has a dose-limiting toxicity attributable to the SB623 cells, then no further patients will be dosed in that cohort until a comprehensive evaluation has been conducted. If 2 of 6 patients in a cohort have a dose-limiting toxicity attributable to the SB623 cells, then no further patients will be dosed in that or higher-dose cohorts. Each dose-limiting-toxicity will be evaluated by the DSMB.

In addition, adverse events attributable to the surgical procedure, such as intracranial infection, intracranial bleeding, or seizures, shall be subject to review by the DSMB

The DSMB shall be the final arbitrator for attributions.

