16.3 Recording of AEs

All AEs, regardless of severity, seriousness, or presumed relationship to Study Drug, must be recorded using medical terminology in the source document and on the CRF. Events will be recorded at all study sites using standard terminology provided by the Sponsor or designate (*e.g.*, CRO), such as COSTART terminology.

The WHO (World Health Organization) Standard Toxicity Criteria (STC) will be used to assist in categorizing and grading adverse events. A copy of the WHO STC will be provided in the study documents. Whenever possible, a diagnosis should be given when signs and symptoms are due to common etiology (*e.g.*, cough, runny nose, sneezing, sore throat, and head congestion should be reported as "upper respiratory infection").

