22.0 APPENDIX C: WHO STANDARD TOXICITY CRITERIA

The WHO Standard Toxicity Criteria is tabulated below in Table 6.

Copies of this document will also be provided to each site as part of the study documents.

For abnormalities not found elsewhere in the WHO table, use the following scale to assign grade or severity:

Grade 1	Mild	Transient of mild discomfort; no limitation in activity; no medical intervention/therapy required.
Grade 2	Moderate	Mild-to-moderate limitation in activity; some assistance may be need. No or minimal medial intervention/therapy required.
Grade 3	Severe	Marked limitation in activity, some assistance usually required; medical intervention/therapy required; hospitalization or prolongation of current hospitalization possible.
Grade 4	Life-threatening	Extreme limitation in activity, significant assistance required; significant medial intervention/therapy required; hospitalization or prolongation of current hospitalization or hospice care probable.

Table 6WHO (World Health Organization) Toxicity Criteria by Grade

Category	Toxicity	Grade 0	Grade 1	Grade 2	Grade 3	Grade 4
Haematology	WBC (x103/l)	4	3.0 - 3.9	2.0 - 2.9	1.0 - 1.9	< 1.0
Haematology	Platelets (x103/l)	WNL	75.0 - normal	50.0 - 74.9	25.0 - 49.9	< 25.0
Haematology	Haemoglobin (g/dl)	WNL	10.0 - normal	8.0 - 9.9	6.5 - 7.9	< 6.5
Haematology	Granulocytes/ Bands (x103/l)	2	1.5 - 1.9	1.0 - 1.4	0.5 - 0.9	< 0.5
Haematology	Lymphocytes (x103/l)	2	1.5 - 1.9	1.0 - 1.4	0.5 - 0.9	< 0.5
Haematology	Haemorrhage	none	mild, no	gross, 1 - 2 units transfusion per episode	gross, 3 - 4 units transfusion per episode	massive, > 4 units transfusion per episode
Coagulation	Fibrinogen	WNL	0.99 - 0.75 x N	0.74 - 0.50 x N	0.49 - 0.25 x N	< 0.25 x N
Coagulation	Prothrombin time(Quick)	WNL	1.01 - 1.25 x N	1.26 - 1.50 x N	1.51 - 2.00 x N	> 2.00 x N
Coagulation	Partial thromboplastin time	WNL	1.01 - 1.66 x N	1.67 - 2.33 x N	2.34 - 3.00 x N	> 3.00 x N
Metabolic	Hyperglycaemia (mg/dl)	< 116	116 - 160	161 - 250	251 - 500	> 500 or ketoacidosis
Metabolic	Hypoglycaemia (mg/dl)	> 64	55 - 64	40 - 54	30 - 39	< 30
Metabolic	Amylase	WNL	< 1.5 x N	1.5 - 2.0 x N	2.1 - 5.0 N	> 5.0 x N
Metabolic	Hypercalcaemia (mg/dl)	< 10.6	10.6 - 11.5	11.6 - 12.5	12.6 - 13.4	13.5
Metabolic	Hypocalcaemia (mg/dl)	> 8.4	8.4 - 7.8	7.7 - 7.0	6.9 - 6.1	6

Category	Toxicity	Grade 0	Grade 1	Grade 2	Grade 3	Grade 4
Metabolic	Hypomagnesaemia (mg/dl)	> 1.4	1.4 - 1.2	1.1 - 0.9	0.8 - 0.6	0.5

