Cardiac	Cardiac ischaemia	none	non-specific T- wave flattening	asymptomatic, ST and T wave changes suggesting ischaemia	angina without evidence of infraction	acute myocardial infarction
Cardiac	Cardiac- pericardial	none	asymptomatic effusion, no intervention required	pericarditis (rub, chest pain, ECG changes)	symptomatic effusion; drainage required	tamponade; drainage urgently required
Cardiac	Hypertension	none or no change	asymptomatic, transient increase by greater than 20 mm Hg (D) or to > 150 / 100 if previously WNL. No treatment required.	recurrent or persistent increase by greater than 20 mm HG (D) or to > 150 / 100 if previously WNL. No treatment required.	requires therapy	hypertensive crisis

Category	Toxicity	Grade 0	Grade 1	Grade 2	Grade 3	Grade 4
Cardiac	Hypotension	none or no change	changes requiring no therapy (including transient orthostatic hypo- tension)	requires fluid replacement or other therapy but not hospitalisation	requires therapy and hospitalisation; resolves within 48 hours of stopping the agent	requires therapy and hospitalisation for > 48 hrs after stopping the agent
Neurologic	Neuro: sensory	none or no change	mild paraesthesias; loss of deep tendon reflexes	mild or moderate objective sensory loss moderate paraesthesias	severe objective sensory loss or paraesthesias that interfere with function	
Neurologic	Neuro: motor	none or no change	subjective weakness; no objective findings	mild objective weakness without significant impairment of function	objective weakness with impairment of function	paralysis
Neurologic	Neuro: cortical	none	mild somnolence or agitation	moderate somnolence or agitation	severe somnolence, (>50 % waking hours), agitation, confusion, disorientation or hallucinations	coma, seizures, toxic psychosis
Neurologic	Neuro: cerebellar	none	slight incoordination, dysdiadochokinesia	intention tremor, dysmetria, slurred speech, nystagmus	locomotor ataxia	cerebellar necrosis
Neurologic	Neuro: mood	no change	mild anxiety or depression	moderate anxiety or depression	severe anxiety or depression	suicidal ideation

Category	Toxicity	Grade 0	Grade 1	Grade 2	Grade 3	Grade 4
Neurologic	Neuro: headache	none	mild	moderate or severe but transient	unrelenting and severe	
Neurologic	Neuro: constipation	none or no change	mild	moderate	severe	ileus > 96 hrs

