7.4.1 Adverse Events

A treatment-emergent adverse event (TEAE) is defined as any event not present prior to study treatment administration or any event already present that worsens in either intensity or frequency following exposure to study treatment.

Adverse events will be classified based on the Medical Dictionary for Regulatory Activities (MedDRA) dictionary, version 15.1 (or higher). Analyses will be conducted on preferred term and primary system organ class (SOC). All adverse event data will be listed per patient including severity, relationship to study treatment, and action taken. Event severity is based on the World Health Organization (WHO) standard toxicity criteria (STC).

A Dose-limiting toxicity (DLT) will be defined as any grade 3 or 4 event which is at least possibly related to study product or administration procedure.

The adverse event reporting period for this trial begins upon receiving the dose of study treatment and ends 24 months after the administration of SB623.

The following summaries of AEs will be provided:

- TEAEs by MedDRA SOC and by preferred term
- TEAEs by maximum severity (mild, moderate, severe, life-threatening) by MedDRA SOC and preferred term
- TEAEs by relationship to study treatment by not related (includes unrelated and unlikely related) or related (includes possibly, probably, and definitely related) by MedDRA SOC and preferred term.
- AEs resulting in discontinuation from the study, by MedDRA SOC and preferred term
- SAEs by MedDRA SOC and preferred term
- The following listings of adverse events will be provided (TEAEs will be denoted in each listing):
 - o All AEs
 - All Dose-Limiting Toxicities (DLTs)
 - o Adverse events resulting in discontinuation from the study
 - o Deaths (if any)
 - o Serious adverse events
 - AE mappings to MedDRA dictionary terms

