7.6 DATA SAFETY AND MONITORING BOARD

The members of the Data Safety and Monitoring Board (DSMB) will be experts who are independent from the sponsor, formed to continuously evaluate toxicity and mortality rates. The procedures and responsibilities for the collection, analysis, and review of the data by the DSMB as well as communication and documentation of their opinions and recommendations are defined in the DSMB charter.

The DSMB will review the safety profile of all patients in each cohort. If the safety profile is deemed acceptable by the DSMB for a given cohort, the first patient in each subsequent cohort will be dosed, beginning 4 weeks after dosing of the last patient of the prior cohort. Two or more serious adverse events will trigger a review by the DSMB before continuing enrollment. Each DLT will be evaluated by the DSMB. The DSMB shall be the final arbitrator for attributions.

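### Appendix C grades haemorrhage by units transfused, so a related intracranial bleed that is evacuated with 1-2 units and no new deficit is Grade 2 and not a DLT

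*Protocol*

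**What the plan says.** **DLT definition.** Protocol synopsis, 9.1 and 14.0, and SAP 3.1, 5 and 7.4.1, require Grade 3 or 4 and at least a possible relation to product or procedure. SAP 6.2 words the threshold as Grade 3 or above.

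**Haemorrhage row (Protocol Appendix C).** Grade 2 is a gross bleed with 1-2 units transfused, Grade 3 is "gross, 3 - 4 units transfusion per episode", and Grade 4 is a massive bleed with more than 4 units. The row does not mention site, evacuation or neurological effect.

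**Generic scale (Appendix C).** It is introduced by "For abnormalities not found elsewhere in the WHO table, use the following scale to assign grade or severity". Its Grade 3 opens with marked limitation of activity and continues with "medical intervention/therapy required; hospitalization or prolongation of current hospitalization possible".

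**Neuro rows (Appendix C).** Motor Grade 3 is "objective weakness with impairment of function" and motor Grade 4 is paralysis. Cortical Grade 4 includes coma and seizures.

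**Status of the table.** Protocol 16.3 says that the criteria "will be used to assist in categorizing and grading adverse events". SAP 7.4.1 bases event severity on them.

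**Oversight.** Protocol 14.0 provides that adverse events attributed to surgery, "such as intracranial infection, intracranial bleeding, or seizures, shall be subject to review by the DSMB", with no grade threshold. SAP 7.6 adds: "Two or more serious adverse events will trigger a review by the DSMB before continuing enrollment". The first-patient hold and the 2-of-6 rule count only DLTs attributable to the cells.

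**The concern.** Safety is the primary objective, DLTs are a listed safety endpoint (SAP 6.2), and the treatment is three needle tracks into the brain. The protocol itself foresees intracranial bleeding (14.0) and craniotomy for haematoma evacuation (2.2.4). The severity of such a bleed lies in where it is and what has to be done about it. Blood volume replaced says little about either, yet it is the only quantity that separates Grades 2, 3 and 4 in the row that names haemorrhage.

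Three outputs are exposed: the DLT endpoint, the DLT listing (Listing 16.2.18.2), and the table of adverse events by maximum severity (Table 14.3.1.2). A bleed that needed a second operation could be missing from the first two and stand as moderate in the third, while also appearing as an SAE. Because the row to use is open in some cases, two sites could also grade the same bleed differently.

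**Working it through.** **1. Which grade does the text give?** Take an intracranial bleed at least possibly related to cells or procedure, and evacuated.

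| Case | Literal grade | DLT? |
|---|---|---|
| 1-2 units, no new deficit | Grade 2 (Haemorrhage row) | No |
| 0 units, no new deficit | No cell fits: Grade 2 starts at 1 unit, and the Grade 1 cell, cut short in the available text, begins with mild | Unclear |
| 3 or more units | Grade 3 or 4 | Yes |
| Fewer than 3 units, with a new deficit | Grade 2 or no cell by Haemorrhage row; up to Grade 3 or 4 by a Neuro row | Depends on row used |

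The generic scale is not available on a literal reading, because haemorrhage is in the table. In the last case, Protocol 16.3 prefers one diagnosis when signs share a cause. That favours a single entry for the bleed over separate neurological entries, and no rule of precedence follows.

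Other rows of the same table do grade by intervention: pericardial effusion that has to be drained and haematuria needing bladder irrigation are both Grade 3.

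**2. The plan's own figure.** Protocol 18.5 gives a chance below 5% of missing a DLT with 6 patients and a true rate of 40%: (1 - 0.40)^6 = 0.60^6 = 0.0467. It reproduces.

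**3. Does under-grading break that figure?** Suppose every evacuation is lost from the DLT count, at the 0.36% rate of Protocol 2.2.4. The countable rate is 0.40 - 0.0036 = 0.3964, and (1 - 0.3964)^6 = 0.6036^6 = 0.0484. This is still below 5%. The limit is a countable rate of 1 - 0.05^(1/6) = 0.3930, a loss of about 0.7 percentage points.

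**4. How likely is such an event?** P(at least one evacuation in 18) = 1 - (1 - 0.0036)^18 = 0.0629. Only a share f would have 1-2 units and no deficit. The documents do not give f, so the values below are assumptions, using 1 - (1 - 0.0036f)^18:

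- f = 25%: 1.6%
- f = 50%: 3.2%
- f = 100%: 6.3%

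The 0.36% comes from a retrospective stereotactic series, not from this procedure. If the true evacuation rate were 1%, 2% or 5% (assumptions), the chance of at least one in 18 would be 16.5%, 30.5% or 60.3%.

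**5. What does one mis-graded bleed do?** Exact (Clopper-Pearson) 95% intervals, assuming no other DLT:

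| | Counted | Not counted |
|---|---|---|
| Cohort | 1/6 = 16.7% (0.4-64.1%) | 0/6 (0-45.9%) |
| Pooled | 1/18 = 5.6% (0.1-27.3%) | 0/18 (0-18.5%) |

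**The case against.** The strongest reply is that patients are protected whatever the grade. Procedural intracranial bleeding goes to the DSMB under 14.0, two or more SAEs trigger a review, procedural complications get expedited reports (16.1), and SAEs and deaths have their own outputs. A bleed attributed purely to surgery could not trip the stopping rules even at Grade 4. All of this stands. A reader might infer that the trial could go on escalating past serious bleeds unseen; the documents do not support that. None of these safeguards, however, puts the event in the DLT listing or corrects its severity grade. The DSMB is named final arbitrator of attribution, not of grade.

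Second, the criteria only assist grading, and the Haemorrhage row sits under Haematology, so a site could sensibly turn to the generic scale or a Neuro row. That is also true. It means under-grading is not certain, but it leaves the choice to each site while the SAP rests severity on the table.

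Third, two broader readings go too far. One is that every bleed with fewer than 3 units is below Grade 3; but a 0-unit bleed has no cell, and one with a deficit can reach Grade 3 or 4 through the Neuro rows. The other is that a related death is excluded from DLTs. Appendix C has no fatal grade, but the SAP 6.2 wording leans towards counting a death. The text is unsettled there and needs a sentence.

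Finally, the SAP plans a DLT listing but its table list has no DLT table, and the intervals above are this review's own. The numerical effect is therefore on a count, not on a planned test.

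**Conclusion.** The point holds in a limited form. For a related intracranial bleed evacuated with 1-2 units and no new deficit, the stated rule gives Grade 2 and leaves it out of the DLT endpoint. For a 0-unit bleed there is no grade, and for a bleed with a deficit there is no precedence rule.

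The effect is mainly on reporting. It reaches the first-patient hold and the 2-of-6 rule only if the DSMB attributes the bleed to the cells. The event is rare: at the cited 0.36% rate, at most a 6.3% chance of any such case in 18 patients, and less if only a share meets the transfusion and deficit conditions. When it happens, it moves a cohort from 1/6 to 0/6.

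A reader might also infer that the sample-size statement fails. At the cited rate it does not (4.84%).

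The conclusion rests on a literal reading of the table and on the transfer of the 0.36% rate to this procedure. It is worth correcting because the correction is cheap and safety is the primary objective.

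**What to change.** Add to Appendix C and SAP 7.4.1:

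> *The Haemorrhage row applies to extracranial bleeding only. Any intracranial haemorrhage that requires surgical evacuation or other medical intervention, or that causes or prolongs hospitalization, is at least Grade 3; otherwise use the generic scale. If a Neuro row gives a higher grade, that grade applies.*

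The explicit Grade 3 floor is needed. Sending these bleeds to the generic scale alone would not do, because its Grade 3 opens with marked limitation of activity, which an evacuated bleed without deficit may not show.

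Align the DLT wording everywhere with the Grade 3 or higher threshold of SAP 6.2, and state that a death at least possibly related to product or procedure is a DLT.

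Apply both to any recorded intracranial haemorrhage before the DLT listing is final. The December 2016 SAP addendum already speaks of final data; if the listing is closed, show the re-grade beside the recorded grade in the clinical report, as a deviation under Protocol 18.6.

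The cost is one table note, aligned DLT wording with one added sentence, and a re-grade of any intracranial bleeds among 18 patients. No new data and no change in sample size are needed. The small downsides are that a few more events may count as DLTs, and that a re-grade made once the data are known must be labelled post hoc.

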23.0 APPENDIX D: COGNITIVE FUNCTION TEST BATTERY

Table 7	Cognitive Function Test Battery
---------	--

Estimated Intelligence
*Wechsler Abbreviated Scale of Intelligence (WASI) 2 Test
Language
Controlled Oral Word Association Category
Vocabulary (WASI)
Attention
Trails A Time
Digit Vigilance Accuracy
Learning and Memory
Rey Auditory Learning Test
Rey Complex Figure – immediate & delayed recall
Logical Memory – WMS-III
Working Memory
Trails B Time and Errors
Letter-Number Sequencing- WMS-III
Visuospatial/Constructional Ability
Rey Complex Figure Copy
Matrix Reasoning—WASI
Psychomotor Efficiency
Digit Vigilance Time
Trails A Errors
Digit Symbol Substitution Test -WAIS-III
Grooved Pegboard
Executive Function (reasoning, mental manipulation)
Stroop Interference
Controlled Oral Word Association—FAS
Mood State and Quality of Life
Beck Depression Inventory, 2 nd Ed.
Beck Anxiety Inventory

* Baseline only

10.2	Clinically Notable Abnormal Values	

AE	Adverse Event
AFP	Alpha-fetoprotein
ATC	Anatomical Therapeutic Class
CEA	Carcinoembryonic antigen
CI	Confidence Interval
CFB	Change From Baseline
DSMB	Data Safety Monitoring Board
DLT	Dose Limiting Toxicity
ESS	European Stroke Scale
FDG	Fluorodeoxyglucose
IHC	inVentiv Health Clinical
HEENT	Head Ears Eyes Nose Throat
ITT	Intent-to-Treat
MedDRA	Medical Dictionary for Regulatory Activities
MRI	Magnetic Resonance Imaging
MRS	Modified Rankin Score
N	Count of Patients
NIHSS	National Institutes of Health Stroke Scale
РВМС	Peripheral Blood Mononuclear Cells
РЕТ	Positron Emission Tomography
SAE	Serious Adverse Event
SAP	Statistical Analysis Plan
SD	Standard Deviation
SOC	System Organ Class
STC	Standard Toxicity Criteria
TEAE	Treatment-Emergent Adverse Event
WASI	Wechsler Abbreviated Scale of Intelligence
WHO	World Health Organization
WHODD	World Health Organization Drug Dictionary

List of Abbreviations and Definitions

1. INTRODUCTION/BACKGROUND

This document describes the statistical methods, data handling procedures, and data presentations to be used in the analysis of data for study SB-STR01. This analysis plan is based on protocol amendment 4.5, dated 22 March 2013.

All statistical analyses and data presentations will be performed by the biostatistics group at inVentiv Health Clinical (IHC) using SAS®, version 9.2 or higher.

2. STUDY OBJECTIVES

2.1 **PRIMARY OBJECTIVE(S)**

To evaluate the safety and tolerability of intracranial administration of SB623 cells. Safety will be determined during 2 years post-implant.

2.2 SECONDARY OBJECTIVE(S)

To evaluate clinical and radiographic response to 3 dose levels of intracranial SB623 cell administration. The major efficacy endpoints will be evaluated at 6 months post-implant; measures will also be taken at 1, 2, 3, 4, 9, 12 and 24 months post-implant.

3. STUDY DESIGN

3.1 OVERVIEW

This is an open-label safety study of stereotactic, intracranial injection of SB623 cells in patients with hemiparesis from stable ischemic stroke who have remained stable during the prior 3 weeks (based on NIHSS assessments at weeks -3 and -1). While primarily a safety study, efficacy parameters will also be evaluated. Three cohorts will receive escalating singe doses of SB623, which are to be stereotactically implanted into grey or white matter sites adjacent to the infarct region. One burr-hole craniostomy will be created, and cells implanted using 3 needle tracks with 5 cell deposits for each track at varying depths around the damaged area. Cell implantation will be standardized as to volume (20 μ L/deposit) and rate (10 μ L/min), with spacing between each implant of approximately 5-6 mm. Each deposit is expected to take approximately 2-3 minutes, with each needle track being completed within 15 minutes. Each cohort will consist of 6 patients defined by an increasing total number of cells implanted. Safety will be monitored by the Investigator, Principal Monitor, Medical Monitor, and an external Data Safety Monitoring Board (DSMB). For the first cohort, a single patient will first be dosed, then evaluated over a 2 week period for safety prior to dosing the next member of the cohort. This 2-week interval will continue between each of the remaining members of the cohort. If the safety profile is acceptable for a cohort, and after review by the DSMB, the first patient in each subsequent cohort will be dosed, beginning 4 weeks after dosing of the last patient of the prior cohort. For the second and third patients in each of the subsequent cohorts, there will be an interval of 2 weeks after the prior patients prior to further enrollment.

SanBio Incorporated Protocol SB-STR01

A dose-limiting toxicity (DLT) will be defined as any grade 3 or 4 events which are at least possibly related to study product or administration procedure. If the first patient in a cohort has a DLT attributable to the SB623 cells, then no further patients will be dosed in that cohort until a comprehensive evaluation has been conducted. If 2 of 6 patients in a cohort have a DLT attributable to the SB623 cells, then no further patients will be dosed in that or other higher-dose cohorts. Each DLT will be evaluated by the DSMB. The DSMB shall be the final arbitrator for attributions.

3.2 STUDY POPULATION

The study population consists of adult patients with hemiparesis from stable ischemic stroke. Stable stroke will be defined as 6-36 mos. post stroke with motor neurological deficit, post-physical therapy, and with no more than ± 1 point change in clinical stroke evaluation (using NIHSS) in the 3 weeks prior to study enrollment. The interval of 6-36 months for this patient population is based on a number of studies that have shown that over 90% of ischemic stroke patients are stable by 90 days post-stroke. The upper limit of 36 months was chosen to allow for the possibility of some brain tissue plasticity remaining, while mainly to increase the potential patient population.

